10.3. Study Completion, Withdrawal, or Lost to Follow-Up

While all efforts will be made to minimize attrition, subjects may withdraw from the study at any time, with or without reason and without prejudice to further treatment. Withdrawn subjects will not undergo any additional study follow-up, nor will they be replaced. All subjects enrolled in the clinical study (including those withdrawn from the clinical study or lost to follow-up) shall be accounted for and documented. When study subjects complete the study per the protocol requirements, their participation in the study is considered as complete, and they will be exited from the study.

If a subject withdraws from the clinical investigation, the reason(s) must be reported. If such withdrawal is due to problems related to device safety or performance, the investigator must ask for the subject's permission to follow his/her status/condition outside of the clinical study. This request needs to be documented in the subject file.

The sponsor may ask that withdrawn subjects are followed for information related to the safety of the device, if available.

Reasons for study exit will be captured in the EDC database and may include, physician discretion, subject choice to withdraw consent, lost to follow-up, or death. While study exit is discouraged, subjects may withdraw from the study at any time, with or without reason, and without prejudice to further treatment.

All applicable case report forms must be completed at study exit (i.e., withdrawal, death, study completion) and an "End of Study" form must be completed. Subjects who are "lost-to-

follow-up" must have documented at least three attempts to contact them prior to completion of the "End of Study" form. Should the subject continue to be unreachable, he or she will be considered to have withdrawn from the study with the primary reason of lost to follow up. Data collected up to the point of subject withdrawal may be used for study analysis unless local regulations prohibit its use.

At the point of study completion and/or withdrawal, all adverse events must be assessed by the investigator. These events must be closed or documented as chronic. For those events that have been assessed as related to the device, these should be followed through resolution if possible and consent has been provided by the subject for data collection on these events.

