7.1. Primary Effectiveness Endpoint

WATCHMAN therapy is non-inferior for the occurrence of stroke (including ischemic and/or hemorrhagic), all cause death, and systemic embolism at 36 months. This endpoint is defined as the Kaplan Meier estimate of time to first occurrence of stroke (including ischemic and/or hemorrhagic), all cause death, or systemic embolism at 36 months.

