13.1.1.3. Statistical Methods

The primary efficacy endpoint event rate from the WATCHMAN FLX Device and Control arms, S₁(t) and S₀(t), respectively, will be estimated by the Kaplan Meier method. The time point of 36 months is defined as the 1095th day post-randomization. The 97.5% one-sided upper bound of confidence limit of the difference between WATCHMAN FLX and Control rates will be calculated using Greenwood formula for the variance of the Kaplan Meier estimates. The objective is met if this confidence limit is less than the predefined noninferiority margin of 5%.

If the non-inferiority hypothesis objective is met, a superiority test will be subsequently performed and a one-sided p-value of 0.025 will be considered significant.

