3.1.2 Sample Size for the Primary Efficacy Endpoint

The power and sample size were calculated employing Farrington Manning methods for non-inferiority using SAS version 9.4. The assumptions and parameters pertaining to this design are as follows:

- Power = 85.9%
- Alpha = 0.025 (one-sided)
- Expected Device and Control group performance: cumulative incidence rate of 10% at 36 months in both groups
- A noninferiority margin $\delta = 5\%$
- Attrition: cumulative attrition rate of 15% in the Device Group and in the Control group at 36 months.

The expected cumulative incidence of 10% at 36 months in the Device group was derived from historical event rates from the PROTECT AF, CAP, PREVAIL, and CAP2 studies. WATCHMAN subjects with previous ablations from these studies experienced a 14.4% event at

3 years. The cumulative incidence is expected to be lower in the OPTION study due to enhanced implant experience over time, device improvements, and a decreased baseline risk profile for subjects enrolled in the OPTION study. The expected cumulative incidence in the Control arm is expected to be equal to that of the Device arm.

The non-inferiority margin of 5% represents a relative risk of 1.5.

Given the above assumptions, 1360 subjects will be required. In order to account for up to 15% expected rate of attrition which includes subjects randomized but not treated and subjects withdrawn or lost-to-follow-up through 36 months, a total of 1600 (1360/(1-0.15)) subjects need to be enrolled.

A sample size of 1600 subjects provides 85.9% power for the Primary Effectiveness Endpoint analysis. Therefore, a maximum sample size of 1600 is determined.

In addition, the power and sample sizes have been re-evaluated for the non-inferiority testing settings that would match the method described to perform the hypothesis analysis, namely, differences in the Kaplan-Meier event rates of the respective endpoints using the Greenwood formula.

The operating characteristics of the statistical test for the primary effective endpoint, and the secondary safety endpoint, are calculated by simulating 10,000 trials, for each endpoint, for a given sample size using custom-written code in SAS. The results are consistent with the sample size calculation performed using a parametric formula, namely the Farrington-Manning method above. The table below presents the simulation results for primary efficacy endpoint.

Power and type I error of the Simulation for Primary Effective Endpoint

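### Protocol 10.3 collects no vital status after exit, so deaths after withdrawal or loss to follow-up are censored out of the primary non-inferiority composite

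*Protocol*

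**What the plan says.** Protocol 10.3 sets the general rule: "Withdrawn subjects will not undergo any additional study follow-up, nor will they be replaced". A subject who cannot be reached after at least three documented attempts falls under the same rule: "he or she will be considered to have withdrawn from the study with the primary reason of lost to follow up". For such a subject, Protocol Table 11.14-1 dates the exit to the last office visit or phone contact.

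Section 10.3 has three exceptions, all tied to the device:
- "If such withdrawal is due to problems related to device safety or performance, the investigator must ask for the subject's permission to follow his/her status/condition", which takes place outside the study;
- "The sponsor may ask that withdrawn subjects are followed for information related to the safety of the device, if available", which is optional;
- events judged device-related, which are followed to resolution where possible and with consent.

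The primary effectiveness endpoint (Protocol 7.1) is "time to first occurrence of stroke (including ischemic and/or hemorrhagic), all cause death, or systemic embolism at 36 months". On timing, Protocol 13.1.1.3 states: "The time point of 36 months is defined as the 1095th day post-randomization". Dropouts are censored at last follow-up (Protocol 13.3.7; SAP 5.6 and 7.3). The sample size assumes a "cumulative attrition rate of 15% in the Device Group and in the Control group" (SAP 3.1.2).

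The plan does address attrition analytically. Protocol 13.3.6 and SAP 5.5 compare the baseline risk of attrition and non-attrition subjects and add a tipping-point analysis. Protocol 13.3.7 and SAP 5.6 add a worst-case analysis for each primary and secondary endpoint. Neither document provides for collecting vital status after exit in either arm.

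**The concern.** Kaplan-Meier is unbiased only if subjects who leave have the same later risk as those who stay. Withdrawal and loss of contact may be linked to failing health. In particular, a subject who has died can fail three contact attempts and, without a records search, be entered as censored at last contact. Death is also the largest component of the composite, so unseen deaths fall on the part of the endpoint that carries most of the events.

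In a non-inferiority comparison, losing events from both arms shrinks the observed difference, and losing more from Device shrinks it further. Both make a false claim of non-inferiority more likely. Losing more from Control works the other way. Without outcomes after exit, the trial cannot show which case holds.

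**Working it through.** **1. The plan's own figures reproduce.** Inputs (SAP 3.1.2): 10% in both arms, margin 0.05, one-sided alpha 0.025, 680 per arm after attrition.
- Farrington-Manning: the restricted null rates are 13.03% and 8.03%, with null SE 0.01659 and alternative SE 0.01627. Power = Φ((0.05 − 1.96 × 0.01659)/0.01627) = 85.9%, as stated.
- Inflation: 1360/(1 − 0.15) = 1600, as stated.
- Kaplan-Meier/Greenwood, 800 per arm, exponential events and 15% exponential attrition (the SAP simulation setting): SE of the difference 0.01564; power = Φ(0.05/0.01564 − 1.96) = 89.2%, against 89.3% simulated. Type I error is 2.5%, against 0.024 simulated.

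**2. Share of the endpoint that is death.** SAP 9.1.1: 35/370 died and 53/370 had the composite; 35/53 = 66%. The component counts (35 + 1 + 18 + 1 = 55) exceed 53 by only 2, so at least 33 of the 53 (62%) had death and no other component.

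**3. Events out of sight with no excess risk.** Per year, event hazard λ = −ln(0.90)/3 = 0.03512 and exit hazard c = −ln(0.85)/3 = 0.05417. The chance of either by year 3 is 1 − 0.90 × 0.85 = 0.235.
- Observed first events: 1600 × 0.235 × λ/(λ + c) = 147.9.
- Event-free exits: 1600 × 0.235 × c/(λ + c) = 228.1.
- Expected first events: 1600 × 0.10 = 160, so 160 − 147.9 = 12.1 fall after exit. About 12.1 × 35/53 = 8.0 of these would be deaths.

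**4. Effect if leavers differ.** Assume the hazard is multiplied by k after exit (the documents give no value). For each arm, solve for λ in

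true rate = 1 − [e^(−3(λ+c)) + ∫₀³ c e^(−(λ+c)u) e^(−kλ(3−u)) du],

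with the true rate on the null boundary: 15% Device, 10% Control. Kaplan-Meier then estimates 1 − e^(−3λ), which is 14.05% (k=2) or 13.27% (k=3) for Device and 9.34% or 8.78% for Control. With D the resulting difference, type I error = Φ((0.05 − D)/SE − 1.96). Example, Device only, k=3: D = 0.0327 and SE = 0.0167 give Φ(−0.92) = 17.8%.

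| Dropout (Device / Control) | Excess hazard in | k=2 | k=3 |
|---|---|---|---|
| 15% / 15% | neither (k=1) | 2.5% | 2.5% |
| 15% / 15% | both arms | 3.7% | 5.0% |
| 15% / 15% | Device only | 8.1% | 17.8% |
| 15% / 15% | Control only | 0.9% | 0.4% |
| 10% / 10% | both arms | 3.3% | 4.0% |
| 10% / 10% | Device only | 5.7% | 10.6% |
| 20% / 10% | both arms | 7.0% | 13.8% |
| 10% / 20% | both arms | 1.8% | 1.4% |

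The 10% and 20% dropout rates are also assumptions.

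**5. What vital status alone would recover.** Suppose deaths after exit are counted and known survivors are treated as event-free to day 1095. The post-exit term becomes e^(−(35/53)kλ(3−u)), with binomial variance. At 15% dropout, type I error is about 3% with no excess hazard, because strokes and emboli after exit are still missed. It is about 4.2% (k=2) or 5.5% (k=3) in the Device-only cases, down from 8.1% and 17.8%.

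**The case against.** **The plan already targets this bias.** It compares the baseline risk of leavers and stayers and adds tipping-point and worst-case analyses, so a reader should not infer that attrition is censored and then ignored. That stands. These analyses, however, measure how much the missing outcomes could matter and do not supply them. The worst case is not defined. If it counts every Device dropout and no Control dropout as an event, about 114 subjects per arm shift the difference by 114/800 = 14 points against a 5-point margin. That would nearly always fail and so says little.

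**The 15% overstates true dropout.** SAP 3.1.2 says up to 15% and includes subjects randomized but not treated. Intent and Attempt subjects stay in scheduled follow-up and in the intention-to-treat analysis (Protocol 10.2.3.1 and 10.2.3.2), so their deaths are not lost. This stands. The true dropout share is not given, and inflation is smaller if it is lower, as the 10% / 10% rows show.

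**A reader might infer that the rule favours the device, with false non-inferiority of 8% or 18%.** The documents do not support that. Those figures need excess risk in Device leavers and none in Control leavers, and nothing in the plan suggests that asymmetry. The same model gives error below 2.5% when only Control leavers are at higher risk.

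**A reader might also infer that follow-up after withdrawal is one-sided and so biases the endpoint.** The exceptions are narrow, one is optional, and nothing says the information enters the primary analysis. They also need not exclude Control subjects, who may receive a device (Protocol 12). Uneven ascertainment is possible but not established.

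**Feasibility.** With up to 150 centres worldwide, and withdrawal of consent among the exit reasons, record searches will not succeed everywhere. The documents give no basis for estimating how complete they would be.

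**Conclusion.** The gap is real and worth closing. Follow-up ends at exit, death is about two thirds of the expected composite, and no vital status is sought in either arm. The size and direction of any resulting bias cannot be known from the plan.

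If exit is unrelated to risk, Kaplan-Meier stays unbiased, type I error stays at 2.5%, and only precision is lost: power would be 91.5% with complete follow-up, against 89.2%. If leavers in both arms carry 2 or 3 times the hazard and 15% truly drop out, error rises to 3.7% or 5.0%. Asymmetric cases run from 0.4% to 17.8%. All of these rest on assumed hazard multipliers, exponential times, and 15% dropout as the upper limit of what the plan allows.

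The sample size is not in question. This is a data-collection weakness that the sponsor should fix; it does not show that the primary comparison is invalid.

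**What to change.** **Protocol 10.3:** add that, for every withdrawn or lost subject in both arms, vital status and date of death through day 1095 are sought from medical or public records where consent and local law permit. Align the consent form with this.

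**SAP 5.5 and 5.6:** add a prespecified analysis of the primary efficacy endpoint that counts these deaths as events. State how survivors are censored when their stroke and embolism status after exit is unknown; treating them as event-free to day 1095 has its own cost (step 5 of the working). Use the recovered vital status in the tipping-point analysis, so that assumed outcomes are needed only for what remains unknown.

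**Cost:** consent wording and modest site effort. Recovery will be incomplete in some countries, and strokes and emboli after exit that are not fatal will still be missed. The required sample size does not change.

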10.4. End of Study Action Plan

At the conclusion of the study, patients receiving a device should be followed per standard of care practices at their site.

11. Study Methods

11.1. Data Collection - Roll-In Subjects

Roll-In subjects must meet all inclusion and none of the exclusion criteria and will not be randomized. For all Intent, Attempt, and Implant subjects (successfully received the WATCHMAN FLX Device) all visits are required, as defined in Table 11.2-1. However, Intent and Attempt subjects do not require LAA imaging at 3 and 12 months. Study procedures and follow-up visits will occur as follows:

Table 11.1-1: Roll-In Study Visits

Visit	Timeframe		
Consent	Must be performed within 40 days prior to implant		
Pre-procedure LAA Imaging (TEE or CT)	- Optional for TEE guided WATCHMAN FLX implants - Required for ICE guided WATCHMAN FLX implants (must be performed after consent and prior to implant). These LAA imaging will be collected according to the Imaging Manual and submitted to the Core Lab for review		
Implant	 Prior ablation (Sequential Group) – The WATCHMAN FLX implant procedure must be performed between 90 and 190 days of the most recent AF ablation procedure Planned ablation (Concomitant Group) – The ablation and WATCHMAN FLX implant must be performed within 40 days of consent 		
3-Month Follow-up	90 ± 15 days from implant		
12-Month Follow-up	365 ± 30 days from implant		
24-Month Follow-up	730 ± 60 days from implant		

Visit	Timeframe
36-Month Follow-up	1095 + 60 days from implant - this follow-up must occur on or after 1095 days and on or before 1155 days

11.2. Data Collection - Randomized Subjects

For all Intent, Attempt, and Implant subjects (successfully received the WATCHMAN FLX Device) all visits are required, as defined in Table 11.2-1. However, Intent and Attempt subjects do not require LAA imaging at 3 and 12 months.

Study procedures and follow-up visits will occur as follows:

Table 11.2-1: Randomized Subject Study Visits

Visit	Timeframe			
Consent	Must be performed within 30 days prior to randomization			
Randomization and Implant	- Prior ablation (Sequential group) – randomization must be performed between 90 and 180 days after the most recent AF ablation procedure. WATCHMAN FLX implant must be performed within 10 days following randomization - Planned ablation (Concomitant group) – the ablation +/- WATCHMAN FLX implant must be performed within 10 days of randomization			
Pre-procedure LAA Imaging (TEE or CT)	- Optional for TEE guided WATCHMAN FLX implants - Required for ICE guided WATCHMAN FLX Implants (must be performed after randomization and prior to implant). These LAA imaging will be collected according to the Imaging Manual and submitted to the Core Lab for review			
3-Month Follow-up	90 ± 15 days from randomization			
12-Month Follow-up	365 ± 30 days from randomization			
24-Month Follow-up	730 ± 60 days from randomization			
36-Month Follow-up	1095 + 60 days from randomization - this follow-up must occur on or after 1095 days and on or before 1155 days			

Note: Baseline data collection not available prior to consent must occur within 30 days prior to randomization. Study-specific procedures that are not standard of care must only be performed after the patient has signed informed consent.

Table 11.2-2: Data Collection Schedule

	Baseline Assessment (Prior to Randomization)	Index Procedure (Ablation Procedure +/- WATCHMAN FLX)	Follow-up Visits****			
Procedure/Assessment			3-Month Follow- up	12-Month Follow- up	24-Month Follow-up	36-Month Follow-up
Informed consent process, including informed consent signature date	X					
Demographics	X					
Physical assessment	X	DG and CC	X	X	X	X
Medical history	X					
Ablation Information	X	CC	0	0	О	0
Device information		DG				
Procedure information and discharge assessment		DG and CC				
TTE	X***					
Pre-procedure LAA imaging (TEE or CT)		DG^				
Implant Procedure TEE/ICE		DG				
Follow-up LAA imaging (TEE or CT)			DG*	DG*	О	О
Brain Imaging (CT or MRI)	O**	O**	O**	O**	O**	O**
Serum Creatinine or GFR/eGFR	X					
Platelet count and Hemoglobin level	X					
NIH Stroke Scale	X		X	X	X	X
Modified Rankin Scale****	X		X	X	X	X
QoL (EQ-5D/SF12)	X			X		X
Medication Regimen Review	X	X	X	X	X	X
Adverse event assessment / device deficiency monitoring (as applicable)	X	X	X	X	X	X

X = All subjects; DG = Device Group; CC = Concomitant; O = Optional, data is collected if available

^{*}Implant subjects only (does not include Intents or Attempts)

^{**} For subjects with prior stroke or TIA, prior MRI/CT scans may be requested by BSC. For subjects who have a neurologic event during the trial, a copy of prior MRI/CT scans and MRI/CT scans from the event may be requested.

^{***} The baseline TTE will be done to evaluate all exclusion criteria to confirm subject eligibility Other recent cardiac imaging may be used to evaluate exclusion criteria if available in the subject's medical record. (see Section 11.10.1 for additional details).

 $^{^{\}wedge} Pre-procedure\ LAA\ imaging\ (TEE\ or\ CT)\ is\ \textit{required}\ for\ ICE\ guided\ WATCHMAN\ FLX\ implants\ and\ \textit{optional}\ for\ TEE-guided\ WATCHMAN\ FLX\ implants.$

Confidential Form/Template 90702637_Rev/Ver AP OPTION Protocol, document # 92320955, Rev E Page 48 of 102

**** Modified Rankin Scale may be completed via telehealth or phone at the discretion of a certified, trained study personnel.

***** Physical exam and NIH stroke scale may not be completed remotely if follow up visit is conducted via phone. QoL may be completed remotely if phone interview script is utilized.

11.3. Study Candidate Screening

Subjects selected for participation in this study may be from the investigator's general non-valvular atrial fibrillation population. Each investigator is responsible for selecting those who are appropriate for inclusion.

All subjects that sign the ICF will be entered in the EDC database. Subjects who sign the ICF but who are not randomized will be considered screen failure subjects and documented as such in the EDC database. Screen failure subjects should be exited immediately upon determining ineligibility.

11.4. Informed Consent

Subjects that have signed and dated the ICF are considered enrolled in the study. The informed consent process must be documented by the person obtaining consent and the documentation must be placed in the subject's file.

11.5. Baseline Assessment Window

Each subject has a maximum of 30 days to complete the baseline assessment following consent. The information below will be documented on case report forms for enrolled subjects:

- Demographics data including age at time of consent, sex, race, and ethnicity
- Medical, cardiac, and neurological history including: cardiovascular diseases; AF
 type (paroxysmal/persistent/long standing persistent) and time since AF diagnosis;
 prior history of ischemic stroke, hemorrhagic stroke and/or TIA; previous cardiac
 procedures; history of bleeding and location; NSAID use; risk factors, including those
 used to calculate HAS-BLED, and CHA2DS2-VASc
- Ablation information including ablation type, success, and rhythm post-ablation
- Physical assessment including vital signs, height, weight, and rhythm
- Current medication regimen review for the use of antiplatelet, anticoagulant, and antiarrhythmic medications
- Modified Rankin Scale (MRS) and NIH Stroke Scale (NIHSS)**
- Quality of Life Questionnaires (SF-12/EQ5D)**
- Serum Creatinine or Glomerular filtration rate (GFR/eGFR). Lab values may come
 from medical record if lab test was performed no greater than 210 days prior to
 randomization. Otherwise, lab values must be obtained during the baseline
 assessment window. Serum creatinine should be recorded if available. If serum
 creatinine is not available but eGFR is, eGFR should be recorded.
- Platelet count and Hemoglobin level. Lab values may come from medical record if lab test was performed no greater than 7 days prior to informed consent. Otherwise, lab values must be obtained during the baseline assessment window.

• Transthoracic Echocardiogram (TTE)*: For echo exclusion criteria assessment of EF, mitral stenosis, pericardial effusion, and PFO.

*Note: The baseline TTE will be done to evaluate all exclusion criteria to confirm subject eligibility. Criteria obtained from a cardiac imaging performed within 180 days prior to randomization may be used if all the exclusion criteria can be evaluated. If all exclusion criteria were not obtained on the prior cardiac imaging, a TTE will have to be conducted at baseline. If a significant cardiac event occurs after the cardiac imaging which causes a change in cardiac status [i.e., major Congestive Heart Failure (CHF) decompensation] the baseline TTE must be repeated after informed consent and prior to randomization

**Note: The person administering the Quality-of-Life Questionnaires and stroke scales should be blinded to the subject's treatment assignment.

